7.1.3 Dose Modifications

In patients with LSF of $\geq 20\%$, the therapeutic dose to the tumor will be modified to ensure <30 Gy to the lungs while maintaining >100 Gy to the tumor if possible.

7.2 Agent Preparation/Handling/Storage/Accountability

7.2.1 Acquisition and accountability

The radiopharmaceutical (Y90) provided for this study will be used only as directed in the study protocol. A trained certified nuclear medicine personnel at EUH or EUHM will receive the shipment and monitor the shipment box as per standard everyday clinical protocols set by Emory Radiation Safety Office. Study site personnel will account for all radiopharmaceutical received at the site. As per protocol, all radioactive materials in nuclear medicine departments will be stored in secure locked hot labs in accordance with the conditions specified on the labels. [name] will maintain an accurate record of dispensing the study radiopharmaceutical in a Drug Accountability Log.

The Drug Accountability Log will record specifics to study drug dispensation such as:

- Records of product delivery, inventory, temperature monitoring, destruction, and return.
- Dosages prepared, time prepared, doses dispensed.
- Doses and/or vials destroyed.

- The Drug Accountability Log will be reviewed by the monitor during site visits and at the completion of the study.

Drug accountability will be noted by the field monitor during site visits and at the completion of the study.

This information must be captured in the source document at each patient visit. Dose changes and interruptions of study drug must be specifically documented in the patient source documents and eCRF.

7.2.2 Formulation, Appearance, Packaging, and Labeling

Each hot lab at EUH or EUHM have their own ⁹⁹Tc generator which will be labelled with MAA according to standard clinical protocol used on a daily basis. The Y90 resin microspheres vials will be delivered at 196 mCi activity on Monday.

7.2.3 Product Storage and Stability

All radioactive materials including ⁹⁹Tc-MAA and Y90 microspheres will be stored in secure locked hot labs at nuclear medicine departments at EUH or EUHM.

7.2.4 Preparation

Each hot lab at EUH or EUHM have their own ⁹⁹Tc generator which will be labelled with MAA according to standard clinical protocol used on a daily basis.

15 mCi of Y90 will be drawn from the 196 mCi vial on Monday to use for the mapping study. The remainder of the 181 mCi activity will decay to 83 mCi by Thursday (Y90 half-life = 64.1 hours). The mother vial will be stored in a clean secure place in hot lab with sterile alcohol swab or paraffin placed on the diaphragm of the vial. After prospective therapeutic dose calculation detailed above, the appropriate activity will be drawn from the mother vial.

7.3 General Concomitant Medication and Supportive Care Guidelines

Patients on vascular endothelial growth factor (VEGF) inhibitors will hold their VEGH inhibitors for 4 weeks prior to mapping angiography. They may resume their medication after Y90 therapy.

7.3.1 Acceptable Concomitant Medications

All treatments that the investigator considers necessary for a subject's welfare may be administered at the discretion of the investigator in keeping with the community standards of medical care. All concomitant medication will be recorded on the case report form (CRF) including all prescription, over-the-counter (OTC), herbal supplements, and IV medications and fluids. If changes occur during the trial period, documentation of drug dosage, frequency, route, and date may also be included on the CRF. All concomitant medications received within 28 days before the first dose of trial treatment and 30 days after the last dose of trial treatment should be recorded. Concomitant medications administered after 30 days after the last dose of trial treatment should be recorded. In

general, concomitant medications and therapies deemed necessary for the supportive care (e.g. such as anti-emetics, anti-diarrhea) and safety of the patient are allowed.

- Medications to prevent or treat nausea or vomiting.
- Anti-diarrheal medications (e.g., loperamide) for patients who develop diarrhea.
- Pain medication to allow the patient to be as comfortable as possible.
- Treatment with bisphosphonates or denosumab for pre-existing, painful bone/liver metastases, and limited-field palliative radiotherapy or surgery is permitted. Patients requiring initiation of such treatment during the course of the study must be evaluated for disease progression; radiotherapy like any concomitant medication must be listed on the CRF.
- Immunosuppressive agents to treat suspected irAEs
- Hematopoietic colony-stimulating growth factors (e.g. G-CSF, GM-CSF, M-CSF), thrombopoietin mimetics or erythroid stimulating agents as per local or published guidelines; in case of anemia, thrombocytopenia or neutropenia, potential immune mediated etiology should be ruled out
- Nutritional support or appetite stimulants (e.g. megestrol).
- Oxygen therapy and blood products or transfusions.
- Inactivated vaccines.
- The patient must be told to notify the investigational site about any new medications he/she takes after the start of the study drug. All medications (other than study drug) and significant non-drug therapies (including physical therapy, herbal/natural medications and blood transfusions) administered during the study must be listed on the Concomitant Medications.

7.3.2 Prohibited Concomitant Medications

During the course of the study, patients must not receive other antineoplastic therapies (e.g. investigational drugs, devices, chemotherapy, immunotherapies) or any other therapies that may be active against cancer or modulate the immune responses. However, limited-field palliative radiotherapy may be allowed as concomitant therapy (see above). The use of systemic steroid therapy and other immunosuppressive drugs is not allowed except for the treatment of infusion reaction, irAEs, and for prophylaxis against imaging contrast dye allergy, standard pre-medication for chemotherapy or replacement-dose steroids in the setting of adrenal insufficiency (providing this is < 10 mg/day prednisone or equivalent), or transient exacerbations of other underlying diseases such as COPD requiring treatment. If systemic corticosteroids are required for the control of infusion reactions or irAEs, it must be tapered and be at non-immunosuppressive doses (< 10 mg/day of prednisone or equivalent) before the next administration of study treatment. If the dose of prednisone or equivalent cannot be reduced to less than 10 mg/day before the administration of next dose of study treatment then the study agent must be discontinued. The use of live vaccines is not allowed through the whole duration of the study. Inactivated vaccines are allowed. There are no prohibited therapies during the post-treatment follow-up period.

7.3.3 Rescue Medications & Supportive Care

Patients whose treatment is interrupted or permanently discontinued due to an adverse event or clinically significant laboratory value, must be followed up at least once a week (or more frequently if required by institutional practices, or if clinically indicated) for 4 weeks, and subsequently at approximately 4-week intervals, until resolution or stabilization of the event, whichever comes first. Appropriate clinical experts such as ophthalmologist, endocrinologist, dermatologist, psychiatrists etc. should be consulted as deemed necessary. All patients must be

followed up for adverse events and serious adverse events until start of new antineoplastic medication or 150 days after discontinuation of study drug, whichever is sooner. Suspected SAEs will continue to be collected beyond the 150-Day safety visit. This will be done by return clinic visits, laboratory checks, and phone calls. The emergence of Immune-Related AE (irAE) may be anticipated based on the mechanism of action of immunomodulatory therapies. Serologic, histologic (tumor sample) and immunological assessments should be performed as deemed appropriate by the Investigator to verify the immune-related nature of the AE and to exclude alternative explanations. Recommendations have been developed to assist investigators in assessing and managing the most frequently occurring irAEs.

7.4 Duration of Therapy

In the absence of treatment delays due to adverse event(s), patients will be treated and followed for 6 months as part of the clinical trial and then at 3 months interval after as per standard of care at Emory IR. This will generally continue until patient's death, enrollment in hospice or loss to follow-up. If there is tumor progression at 3 months, patient may ensue other liver directed or systemic therapies.

In the event of a patient's withdrawal, the Investigator will make every effort to complete the End of Treatment procedures specified in the Schedule of Events.

7.4.1 Treatment Beyond Progression

In this study, patient will only be treated once unless the entire tumor is covered by the initial Y90 radioembolization therapy. In that case, the patient will undergo a second Y90 therapy in 4 weeks assuming eligibility criteria are maintained. If there is tumor progression at 3 months, patient may ensue other liver directed or systemic therapies.

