1.3 Schedule of Activities (SoA)

Study Flow Chart for Individual Patients

Estimated Timeline for Weeks 1-2 (Mapping and Treatment Week)

Monday:

7:30 AM-9:30 AM: 1st Angiographic study for mapping and MAA delivery

10:00 AM-11:00 AM: MAA SPECT/CT (Patient will go to nuclear medicine with radial/femoral arterial access sheath in place)

11:30 AM-1:00 PM: 2nd Angiographic study for low-dose Y90 delivery (After the procedure, patient's femoral sheath will be removed and hemostasis will be achieved with manual compression or closure device. If procedure performed via radial access, which is more commonly performed currently at Emory, the radial sheath will stay in and removed according to IR protocol after Y90 SPECT/CT.)

2:00 PM-3:00 PM: Y90 Bremsstrahlung SPECT/CT

3:00 PM-3:30 PM: Removal of the radial sheath at IR post procedural area and discharge.

4:30-5:30 PM: Y90 PET/CT.

Patient is free to go home after this.

Thursday:

11:00 AM-12:30 PM: 3rd angiographic study to deliver therapeutic dose of Y90.

1:00 PM-2:00 PM: Y90 Bremsstrahlung SPECT/CT (After the procedure, patient's femoral sheath will be removed and hemostasis will be achieved with manual compression or closure device. If procedure performed via radial access, which is more commonly performed currently at Emory, the radial sheath will stay in and removed according to IR protocol after Y90 SPECT/CT.)

3:00 PM-3:30 PM: Removal of the radial sheath at IR post procedural area and discharge.

4:30-5:30 PM: Y90 PET/CT.

Patient is free to go home after this.

Study Procedures	Screening Visit Week 0	Therapy planning/mapping Week 1-2	Y90 sirsphere treatment Week 1-2	1 week post procedure Week 6	1 month post procedure Week 6	3 months post-procedure Week 14	6 months post-procedure Week 26
Informed consent	X						
Entry Criteria	X						
Demographics	X						
Medical/surgical Hx	X						
Blood sampling	X				X	X	X
Collect list of medications	X						
Vital signs	X						
Physical exam	X						
Phone follow-up by [name] or Research Nurse				X			
MRI W & WO contrast	X				X	X	X
Conventional MAA angiography		X					
Low dose Y90 shunt study angiography		X					
SPECT/CT		X	X				
PET/CT		X	X				
Y90 Treatment			X				
Post Procedure Clinic follow up					X	X	X

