Radial or femoral arterial access will be obtained. A 5 Fr catheter will be used to select superior mesenteric artery and celiac trunk. A 2.8 Fr microcatheter will be advanced to the right or left hepatic artery branch supplying the targeted HCC lesion(s). From this location, detailed evaluation of hepatic arterial vasculature using conventional angiography and 3D cone beam CT (CBCT) will be performed to ensure complete perfusion of the targeted tumor(s) and absence of visible non-target embolization. If a potential non-target vessel (i.e. gastroduodenal or right gastric artery) is observed, the vessel will be embolized using coils or plugs during the first mapping study using MAA. From the catheter location where CBCT will be performed to ensure complete perfusion of the tumor and lack of non-target supply. Then MAA, low-dose or therapeutic dose Y90 will be administered.

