The shunt studies will be performed by [name] on Mondays for reasons explained below. Radial or femoral arterial access will be obtained. A 5 Fr catheter will be used to select superior mesenteric artery and celiac trunk. A 2.8 Fr microcatheter will be advanced to the right or left hepatic artery branch supplying the targeted HCC lesion(s). From this location, detailed evaluation of hepatic arterial vasculature using conventional angiography and 3D cone beam CT (CBCT) will be performed to ensure complete perfusion of the targeted tumor(s) and absence of visible non-target embolization. If a potential non-target vessel (i.e. gastroduodenal or right gastric artery) is observed, the vessel will be embolized using coils. From the catheter location where CBCT was performed, 4 mCi of Tc^{99m} MAA will be administered. **The catheters will be removed, and the arterial access sheath will be secured in place. This is commonly done for our out of town or out of country patients at Emory in whom both mapping and Y90 is performed on the same day. Before the patient leaves the IR suite, all the catheters will be removed. The sheath is gently sutured to the overlying skin. Multiple tegaderms will be applied. Additionally, for the radial access cases, an arm-board will be applied. When taking all the pre-cautions detailed above, we have not experienced any accidental dislodgment during patient transport/waiting.** The patient will be then transferred to nuclear medicine department for ^{99m}Tc MAA planar and SPECT/CT of the chest and abdomen.

C. ^{99m}Tc MAA Planar and SPECT/CT of chest and abdomen (Monday)

Planar and SPECT/CT of chest and abdomen will be obtained with low energy filter according to our standard clinical protocol at Emory. The patient will be then transferred back to IR for 2nd mapping angiography and administration of low-dose Y90. **Quantitative reconstruction of SPECT/CT with Tc-99m is available with MIM Software[40].**

D. 2nd Mapping Angiography and Administration of low dose Y90 (Monday)

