v. **Y90 Activity for administration (GBq) = Targeted Liver Lobe Activity (GBq) X (1+LSF)**

Lung dose after therapeutic Y90 RE will be calculated using the following formula:

vi. **Lung Dose (Gy) = Y90 Activity to be Administered (GBq) X LSF X 50 / Mass of Lungs (Kg)**

Lung Dose <30Gy will be ensured by reducing administered activity if needed (lung mass assumed at 1 Kg)[8].

H. 3rd Angiography and Administration of Y90 Therapy Dose (Wednesday/Thursday)

The actual prescribed Y90 activity as calculated above using MAA SPECT (**the current standard of care**) will be administered on Wednesday or Thursday of the same week after the shunt study. The desired activity will be drawn from the remainder of activity in the 5-day flex resin microsphere vial. It will be administered by [name] using the same catheter techniques described above. **After the procedure, patient's femoral sheath will be removed and hemostasis will be achieved with manual compression or closure device. If procedure performed via radial access, which is more commonly performed currently at Emory, the radial sheath will stay in and removed according to IR protocol after Y90 SPECT/CT.** The patient will be then transported to nuclear medicine department of Y90 SPECT/CT.

I. Therapeutic-dose Y90 Planar and SPECT/CT (Wednesday/Thursday)

Using the same technique described above (section E), planar and SPECT/CT will be performed using medium energy filter. The patient will then be discharged from IR after removal of the radial sheath according to our standard protocol.

J. Therapeutic-dose Y90 PET/CT of chest and abdomen (Wednesday/Thursday)

The patient will then undergo time of flight Y90 PET/CT with one or two bed positions depending on the patient's size. This will also occur on the same day and at the same location as the remainder of mapping day either at EUH or EUHM.

Below is the conservative estimated timeline of Mapping/shunt studies performed on Wednesday or Thursday:

11:00 AM-12:30 PM: 3rd angiographic study to deliver therapeutic dose of Y90.

1:00 PM-2:00 PM: Y90 Bremsstrahlung SPECT/CT (After the procedure, patient's femoral sheath will be removed and hemostasis will be achieved with manual compression or closure device. If procedure performed via radial access, which is more commonly performed currently at Emory, the radial sheath will stay in and removed according to IR protocol after Y90 SPECT/CT.)

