3:00 PM-3:30 PM: Removal of the radial sheath at IR post procedural area and discharge.

4:30-5:30 PM: Y90 PET/CT at Cardiac PET center on the 4th floor of EUHM.

Patient is free to go home after this.

K. Y90 Therapy Tumor, Liver, and Lung Dose Calculation (Friday)

Utilizing the MIM software, post Y90 therapy PET/CT data and partition method described above, the mean actual dose delivered to the tumor, normal liver, and lung will be calculated by Drs. [name] and [name]. The software will generate ROIs from the inside to the periphery of the tumor based on Y90 delivery, and Dose Volume Histograms (DVH) plotting the delivered dose as a function of liver volume. Using DVH, % of tumor volume receiving >100Gy and dose range to the tumor will be also calculated.

L. Follow-up phone call [REDACTED] or study nurse (1-week post therapy)

Patient will be followed by phone to ensure they are doing well, and they will be screened for any symptoms related to adverse events. If any concerning symptoms is reported, they will be brought to IR clinic for further evaluation.

M. 1-Month clinical and Imaging Follow-up

- Multiphase liver mass protocol MRI or CT will be obtained
- Brief medical history
- Symptom-directed physical exam
- ECOG Performance Status
- Vitals signs
- Review of prior/concomitant medications
- Clinical laboratory tests for:
 - Hematology
 - CMP

N. 3-Month clinical and Imaging Follow-up

- Multiphase liver mass protocol MRI or CT will be obtained
- Brief medical history
- Symptom-directed physical exam
- ECOG Performance Status
- Vitals signs
- Review of prior/concomitant medications
- Clinical laboratory tests for:
 - Hematology
 - CMP

O. 6-Month clinical and Imaging Follow-up

- Multiphase liver mass protocol MRI or CT will be obtained
- Brief medical history
- Symptom-directed physical exam
- ECOG Performance Status

- Vitals signs
- Review of prior/concomitant medications
- Clinical laboratory tests for:
 - Hematology
 - CMP

End of Treatment

End of treatment is defined as the last planned Y90 therapy within the 6-month dosing period. For subjects who discontinue drug treatment prior to 6 months, end of treatment is considered the last visit where the decision is made to discontinue treatment. All required procedures may be completed within \pm 7 days of the end of treatment visit. Repeat disease assessment is not required if performed within 28 days prior to the end of treatment visit.

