10.4 Analysis of Secondary Endpoints

1. To Identify tumor dose response thresholds (TDRT) and tumor dose distribution in patients with HCC treated with Y90 resin microspheres.

All patients will undergo baseline liver mass protocol abdominal MRI without and with contrast within 30 days prior to the shunt study, and 1, 3, 6, and 12 months after Y90 RE therapy.

Objective TR will be evaluated longitudinally using mRECIST criteria by [name] with a help of an abdominal radiologist. TDR will be calculated using two different methods: 1. Mean dose of the entire tumor resulting in objective TR; 2. Determination of % tumor volume receiving >100 Gy resulting in objective TR. The reason for the second TDR calculation is to take into account the non-homogeneity of Y90 dose delivered to the tumors previously reported.[27, 28] TDR threshold based on logistic regression will be determined by Drs. [name], [name], and [name].

2. To optimize low dose Y90 techniques in predicting TNR and LSF.

No statistical consideration was deemed necessary for this secondary endpoint.

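### Section 7.4.1 inverts the re-treatment rule: as worded, a fully covered tumor gets a second Y90 therapy at 4 weeks and an incompletely covered tumor does not

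*Combined protocol and SAP*

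**What the plan says.** Section 7.4.1 sets the number of therapies per patient. The default is one: the "patient will only be treated once unless the entire tumor is covered by the initial Y90 radioembolization therapy". The next sentence gives the consequence of the exception: "In that case, the patient will undergo a second Y90 therapy in 4 weeks assuming eligibility criteria are maintained".

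Other sections bear on how the rule should read:

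- **Technique (sections 7.1.2 and 8.1).** Angiography and cone beam CT at the chosen catheter position "will be performed to ensure complete perfusion of the targeted tumor(s) and absence of visible non-target embolization". Section 7.1.2 places this check ahead of every injection: "Then MAA, low-dose or therapeutic dose Y90 will be administered". Section 8.1 has the therapeutic dose given "using the same catheter techniques described above".
- **Schedule (section 1.3).** The table has one treatment column, "Y90 sirsphere treatment Week 1-2".
- **End of treatment (section 8.1).** "End of treatment is defined as the last planned Y90 therapy within the 6-month dosing period". This leaves room for more than one therapy but sets no condition for a second.

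**The concern.** The exception is attached to the wrong group. A second therapy makes clinical sense when the first has left part of the tumor untreated. The sentence instead makes it mandatory when nothing was left untreated, and provides none when something was.

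This is an operative treatment rule. Followed literally, it gives patients with covered tumors another angiography and another radioactive dose without need. Patients with incomplete coverage would get no second Y90 therapy; the only later option section 7.4.1 names for them is other treatment if the tumor progresses at 3 months. If operators follow common sense instead, each sensible decision becomes a departure from the written protocol.

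Safety is part of the primary objective (sections 3 and 10.1), so adverse events from unneeded second therapies would enter the trial's safety results.

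**Working it through.** The plan states no figure to reproduce. The check is of the logic of the rule, and then of whether any other text corrects it.

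**Step 1: parse the rule.** The form is *once, unless A; in case A, a second therapy*, where A is full coverage of the tumor by the first therapy.

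| Coverage by first therapy | As written | Apparent intent |
|---|---|---|
| Entire tumor covered | Second therapy at 4 weeks | One therapy |
| Not entirely covered | One therapy | Second therapy at 4 weeks |

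Both second-therapy cells are subject to the eligibility re-check.

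**Step 2: compare with the rest of the plan.**

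- The perfusion check makes full coverage the intended result of the first therapy. Under the literal rule, the exception would then describe the usual patient, and the single-treatment default would describe the unusual one.
- The schedule plans one Y90 treatment, in week 1-2.
- Sections 7.2.4 and 8.1 describe one vial per patient, used for mapping and for one therapy in the same week.
- The end-of-treatment definition is consistent with an occasional second therapy but does not say who receives it.
- No readable section gives a reason to re-treat a covered tumor, and none states the condition in the opposite direction.

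**Step 3: ask whether the eligibility re-check repairs the rule.** None of the criteria in section 5.1 concerns coverage. The re-check may lower the number re-treated, but it does not change which group is selected.

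**Step 4: illustrate the scale.** Inputs: N = 30 (section 1.1) and p, the share fully covered by the first therapy. The documents do not give p; the values below are assumptions. Before the eligibility re-check:

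- re-treated as written = 30 × p
- re-treated under the corrected rule = 30 × (1 − p)

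| p (assumed) | As written | Corrected |
|---|---|---|
| 0.7 | 21 | 9 |
| 0.8 | 24 | 6 |
| 0.9 | 27 | 3 |
| 1.0 | 30 | 0 |

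Since 30p + 30(1 − p) = 30 for any p, the two rules are exact complements: before the re-check, each patient is assigned the opposite number of therapies under one rule from the other.

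**Step 5: identify what is and is not affected.** LSF and TNR for the MAA versus low-dose Y90 comparison are measured at mapping, before any therapy. PFS and OS are timed from first dose or start of protocol therapy (sections 9.1.2 and 10.5.4), so their starting points do not move. The listed risks are small: under 1% for the main events in section 2.3, and about 2% for gastric or duodenal ulcer in section 11.1. However, section 11.1 also lists earlier liver-directed therapy among the settings in which reduced activity should be considered because of radioembolization-induced liver disease. The 50 Gy liver limit in section 7.1.2 is written for a single activity calculation, with no cumulative rule.

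**The case against.** The strongest reply is that the slip corrects itself in context. The trial is run at one center with monthly adherence meetings (sections 4.1 and 13.2), and an experienced operator would probably see that the literal rule makes no sense. That is fair as to likelihood. It does not justify leaving a radiation-treatment rule that is safe only if staff disregard its wording.

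A second reply concerns eligibility. Criterion s in section 5.1 requires earlier cancer therapy to have ended at least 12 weeks before study therapy. If the first Y90 counted as earlier therapy, a second at 4 weeks would fail the criterion and nobody would be re-treated. The criterion more naturally means therapy before the study. On the other reading it would block the second therapy under either wording, leaving the clause without effect but no less inverted.

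Three limits stand:

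- The intended rule is inferred, and the study schema and patient flow chart are not readable in the text available, so a re-treatment branch shown there cannot be excluded.
- The counts rest on assumed coverage rates and are not evidence of how many patients would be affected.
- Correcting the condition does not settle whether follow-up visits run from the first or the second therapy, or which dose enters the first threshold method in section 10.4 ("Mean dose of the entire tumor resulting in objective TR") for a patient treated twice. Those questions arise under either wording and carry no weight here.

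**Conclusion.** The concern holds. The re-treatment condition in section 7.4.1 is wrong as written: it selects fully covered tumors for a second Y90 therapy and excludes incompletely covered ones. The literal meaning is certain; the intended opposite is a well-supported inference.

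The number of patients affected cannot be stated without a coverage rate. Over the assumed range of 70% to 100% coverage, and before the eligibility re-check, 21 to 30 of 30 patients would be re-treated as written, against 9 to 0 under the corrected rule. The consequence is for patient safety and protocol adherence; the LSF/TNR comparison is untouched. The sentence should be corrected because it decides who receives a second radiation treatment.

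**What to change.** Replace the two sentences in section 7.4.1 with wording such as: *Each patient receives one Y90 therapy. If that therapy does not cover the entire tumor, a second is given 4 weeks later, provided the patient still meets the eligibility criteria.* The investigator should confirm that this is the clinical intent. This is clearer than inserting the word *not*, because saying that the entire tumor is not covered could be read as none of it being covered.

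Optionally, add a sentence to section 10.4 saying whether the dose-response threshold for a re-treated patient uses the summed delivered dose or only the response imaged before the second therapy.

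The cost is one reworded rule and, if wanted, one clarifying sentence. The rewording needs no change to sample size, planned visits or the primary analysis.
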